3.2 Exclusion Criteria

A subject who meets any of the following criteria is ineligible for the study:

- 1) The subject has received cytotoxic chemotherapy (including investigational cytotoxic chemotherapy) or biologic agents (e.g., cytokines or antibodies) for urothelial cancer within 4 weeks, or intravesical BCG within 6 weeks of the first dose of study treatment.
- 2) Prior treatment with any PD-1 or PDL-1 inhibitor
- 3) The subject has received therapeutic radiation:
 - a. to the bladder/prostate/rectum pelvis
 - b. to any other site(s) within 28 days of the first dose of study treatment
- 4) Obstructive renal failure that is not relieved with stents or nephrostomy tube/s.

- 5) The subject has received any other type of investigational agent within 28 days before the first dose of study treatment.
- 6) Steroid doses greater than an equivalent of prednisone 10 mg daily
- 7) Uncontrolled hematuria
- 8) The subject has uncontrolled, significant intercurrent or recent illness including, but not limited to, the following conditions:
 - a. Cardiovascular disorders such as uncontrolled arrhythmias or uncontrolled congestive heart failure.
 - b. Gastrointestinal disorders particularly those associated with a high risk of perforation or fistula formation including:
 - i. Any of the following at the time of screening
 1. active peptic ulcer disease,
 2. active inflammatory bowel disease (including ulcerative colitis and Crohn's disease), diverticulitis, cholecystitis, symptomatic cholangitis or appendicitis
 - ii. Any of the following within 6 months before the first dose of study treatment:
 1. history of abdominal fistula
 2. Bowel perforation
- 9) The subject has a previously identified allergy or hypersensitivity to components of the study treatment formulation.
- 10) The subject is unable or unwilling to abide by the study protocol or cooperate fully with the investigator or designee.
- 11) Presence of another invasive malignancy, which required systemic therapy within 12 months of protocol enrollment, except for resected skin cancers or prostate cancer that is in remission.
- 12) Pregnant or nursing women

- 13) Patient is a candidate for radical cystectomy as a potentially curative option. The patient may not be a candidate for radical cystectomy due to any of the following reasons: comorbidities, patient preference, or physician discretion.
- 14) Patients with inherited syndromes associated with hypersensitivity to ionizing radiation (e.g., Ataxia-Telangiectasia, Nijmegen Breakage Syndrome)

4.0 STUDY ASSESSMENTS

4.1 Pre-Treatment Period

During the Pre-Treatment Period, subjects are consented and qualified (screened) for the study. Informed consent must be obtained before initiation of any clinical screening procedure that is performed solely for the purpose of determining eligibility for this study. Evaluations performed as part of routine care before informed consent can be considered as screening evaluations if done within the defined screening period, and if permitted by the site's institutional review board (IRB)/ ethics committee (EC) policies. Informed consent may be obtained within 42 days prior to first dose of study treatment. At informed consent, subjects will be assigned a subject identifier at time of registration.

For each subject, the Pre-Treatment Period ends upon receipt of the first dose of study treatment or final determination that the subject is ineligible for the study.

4.2 Study Treatment Period

Pregnancy Test: In Women of child Bearing Potential (WOCBP) prior to dosing nivolumab. A serum or urine pregnancy testing is required within 7 days of study enrollment, then every 6 weeks. [more frequently if required by local standard]. After discontinuation from nivolumab these should be repeated at approximately 30 days and approximately 70 days [or more frequently if required by local standard].

Laboratory testing prior to each dose: Within 72 hrs prior to re-dosing to include CBC w/ differential, LFTs (ALT, AST, total bilirubin, alkaline phosphatase), BUN or serum urea level, creatinine, Ca, Na, K, Cl, Glucose, TSH (with Free T4 and Free T3). Thyroid function testing should be done at weeks 7 and 13, and then 6 and 12 months post

enrollment. If the subject is unable to have a study assessment taken within the defined time window due to an event outside of his or her control (e.g., clinic closure, personal emergency, inclement weather, vacation), the assessment should be performed as close as possible to the required schedule.

Subjects should be instructed to inform the investigator of any AEs. Subjects experiencing dizziness, sleepiness, or other symptoms that could influence alertness or coordination should be advised not to drive or operate other heavy machinery.

Subjects may receive study treatment until the earlier of PD or unacceptable toxicity. Regular tumor assessments including cystoscopies and biopsies should be performed according to the protocol guidelines if patient discontinues study therapy due to toxicities and if feasible per their medical status.

The Treatment Period ends when a subject receives his or her last dose of study treatment; the subject then enters the Post-Treatment Period.

4.3 Post-Treatment Period

Subjects will be followed per protocol guidelines. If patients have residual or progressive disease noted during evaluation in the first 12 months, requiring other therapeutic modalities, then they will enter follow up phase. Additional follow-up will occur for subjects with AEs related to study treatment that are ongoing at every visit, and for subjects with SAEs related to study treatment that occur after the time of this visit.

4.4 Laboratory Assessments

Local laboratories will perform all laboratory tests. Blood samples for standard hematology and serum chemistry will be done using standard procedures. Surveillance cystoscopies and biopsies as indicated are recommended every 3 months during the first 12 months after starting study therapy.

A cystoscopy and biopsy should be performed at any time prior to study entry, 13 weeks, 6 months, and 12 months after start of study treatment. At 9 months cystoscopy needs to be done and biopsies are done if clinically indicated and send archival slides if available. These assessments are considered standard of care and maybe delayed +/-28 days per

insurance requirements. Archival slides from pre-therapy biopsy and from week 13, 6 months, and 12 months need to be sent to:

[name].
Karmanos Cancer Institute
[name]
Correlative Sciences Lab Rm 808
[contact]
E-mail: [contact]

[name]
Karmanos Cancer Institute
[name]
Correlative Sciences Lab Rm 808
[contact]
Email: [contact]

4.5 Tumor Assessment

Response criteria:

For measurable disease in the bladder and/or lymph node/s, RECIST criteria 1.1 will be used [14].

THE RECIST 1.1 CRITERIA WITH UNIDIMENSIONAL MEASUREMENT ARE TO BE USED FOR MEASURABLE DISEASE RESPONSE EVALUATION

Methods of Assessment

The same method of assessment and the same technique should be used to characterize each identified and reported lesion at baseline and during follow-up. CT is the best currently available and reproducible method to measure lesions selected for response assessment. MRI is also acceptable in certain situations (e.g., for body scans but not for lung). Lesions on a chest X-ray may be considered measurable lesions if they are clearly defined and surrounded by aerated lung. However, CT is preferable.

Baseline Disease Assessment

All baseline evaluations should be performed as closely as possible to the beginning of treatment and never more than 42 days before the beginning of the treatment.

Measurable lesions must be accurately measured in at least one dimension (longest diameter in the plane of measurement is to be recorded) with a minimum size of:

- 10 mm by CT scan (CT scan slice thickness no greater than 5 mm; when CT scans have slice thickness >5 mm, the minimum size should be twice the slice thickness).
- Malignant lymph nodes: To be considered pathologically enlarged and measurable, a lymph node must be ≥ 15 mm in short axis when assessed by CT scan (CT scan slice thickness is recommended to be no greater than 5 mm). At baseline and in follow-up, only the short axis will be measured and followed.

Non-measurable lesions

Non-measurable lesions are all other lesions, including small lesions (longest diameter <10 mm or pathological lymph nodes with 10 to <15 mm short axis), as well as truly non-measurable lesions.

Target Lesions

- All measurable lesions up to a maximum of two lesions per organ and five lesions in total, representative of all involved organs, should be identified as target lesions and recorded and measured at baseline.
- Target lesions should be selected on the basis of their size (lesions with the longest diameter) and be representative of all involved organs, as well as their suitability for reproducible repeated measurements.
- All measurements should be recorded in metric notation using calipers if clinically assessed. A sum of the diameters (longest for non-nodal lesions, short axis for nodal lesions) for all target lesions.

Non-target Lesions

All lesions (or sites of disease) not identified as target lesions, including pathological lymph nodes and all non-measurable lesions, should be identified as non-target lesions and be recorded at baseline. Measurements of these lesions are not required and they should be followed as 'present', 'absent' or in rare cases, 'unequivocal progression'.

Evaluation of target lesions

Complete Response (CR):

Disappearance of all target lesions. Any pathological lymph nodes (whether target or non-target) must have reduction in short axis to <10 mm.

Partial Response (PR):

At least a 30% decrease in the sum of diameters of target lesions, taking as reference the baseline sum of diameters.

Progressive Disease (PD):

At least a 20% increase in the sum of diameters of target lesions, taking as reference the smallest sum on study (this may include the baseline sum). The sum must also demonstrate an absolute increase of at least 5 mm.

Stable Disease (SD):

Neither sufficient shrinkage to qualify for PR nor sufficient increase to qualify for PD.

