2.3 Study Calendar

Prestudy labs, physical exam and EKG should be done within 28 days of day 1. Day 1 labs can be done within 3 days of day 1. A window of +/- 3 days is permitted for the days of nivolumab therapy.

Testing	Pre study	Wk 1	Wk 3	Wk 5	Wk 7	Wk 9	Wk 11	Wk 13	Wks 15,17, 19,21, 23,25	6, 9 and 12 mths ⁴
H and P	X	X	X	X	X	X	X	X	X	X
VS, Wt	X	X	X	X	X	X	X	X	X	X
PS	X	X	X	X	X	X	X	X	X	X
Tox	X	X	X	X	X	X	X	X	X	X
Labs ¹	X	X	X	X	X	X	X	X	X	X
TSH, free T3/T4	X				X			X		X
ECG ²	X									
Cystoscopy ⁷	X							X		X

Biopsy ⁷	X							X		X
CT/MRI ³ of abdomen/pelvis	X							X		X
CXR/ chest CT ³	X									
Nivolumab		X	X	X	X	X	X	X	X	
visits during RT ⁵		X	X	X	X	X				
PFS/OS ⁶		X	X	X	X	X	X	X	X	X
Biomarkers ³	X				X			X		X
QOL questionnaires ³	X	X	X	X	X	X	X	X	X	X

1. Labs include: CBC diff, platelets, Electrolytes, BUN, creatinine, glucose, Albumin, alkaline phosphatase, total bilirubin, calcium, total protein, SGOT, SGPT. Pregnancy test for women of child bearing potential within 7 days of study enrollment and every 6 weeks thereafter.
2. ECG at screening and repeat if clinically indicated.
3. ICF, Baseline biomarkers, QOL questionnaires and all tumor evaluation/measurement scans must be within 42 days prior to treatment. CT/MRI of abdomen and pelvis is required for pretreatment and subsequent tumor assessments. CXR/CT chest is required at screening only to evaluate for metastases. Biomarkers should be collected at time of PD.
4. 6, 9 and 12 month visits will be from start of therapy. A window of +/- 28 days is permitted for these visits.
5. RT will be done **continuously** daily Monday to Friday (except for weekends and holidays) for a total of 32-35 fractions from week 1 to week 8. The time period of 8 weeks is a maximum duration as the radiation fractions can get delayed due to holidays, machine downtime, patient cancellation due to transportation etc. During RT patients should be evaluated for toxicity at a minimum every other week. Nivolumab should be started +/- 3 days of first day of RT.

6. After 12 months the patients will be followed for PFS and OS every 3 months for a maximum of 5 years.

7. Screening cystoscopy and biopsy can be performed within 6 months of day 1. On study cystoscopy will be done at week 13 and at months 6, 9 and 12 +/- 28 days. Biopsies will be required at week 13, month 6 and month 12 +/- 28 days. Month 9 biopsies done if clinically indicated.

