3.0 STUDY POPULATION

3.1 Inclusion Criteria

- 1) Localized urothelial cancer of bladder with presence of transitional cell carcinoma (TCC) component. Mixed histologies are allowed.
- 2) Clinical or pathologic stage T2 –T4 disease including T4a and 4b if feasible to treat with radiation therapy.
- 3) Locoregional lymph node metastases are permitted but patients with distant metastases are ineligible. Imaging to evaluate for distant metastases should consist of a minimum of CT/MRI of abdomen/pelvis or CT urogram and a CXR or CT chest. Patients for which there is clinical suspicion or symptoms of bone metastasis should have a bone scan completed to rule out metastatic disease prior to enrollment on study.
- 4) Agreeable to consider radiation therapy (RT) for the urothelial cancer: patients have to be evaluated by a radiation oncologist and deemed to be candidates for RT.
- 5) The patients must not be candidates for chemotherapy due to at least one of the following reasons:
 - a. Performance status of 2
 - b. Creatinine clearance \leq 60 ml/min as calculated by the Cockcroft-Gault formula.
 - c. Cardiac disease such as NYHA Class III or IV heart failure or cardiac ischemia within the last 12 months, grade 2 or greater neuropathy, or other

comorbidities based on which patient is not considered a candidate for chemotherapy.

- 6) Adequate liver function with alkaline phosphatase, AST and ALT ≤ 3 x upper limit of normal and bilirubin < 1.5 x ULN
- 7) Adequate Bone marrow function defined as absolute neutrophil count $\geq 1500/\text{mm}^3$ and hemoglobin ≥ 9 g/dL and platelets $\geq 100\text{K}/\text{mm}^3$.
- 8) PS of 0-2 by Zubrod score
- 9) Life expectancy of 12 months
- 10) Age ≥ 18 years of age
- 11) Willingness to sign informed consent
- 12) Patients cannot have active autoimmune disease or immunosuppressive conditions.
- 13) Serum creatinine ≤ 1.5 X institutional ULN or creatinine clearance > 40 ml/min as calculated by the Cockcroft-Gault formula.
- 14) In females with childbearing potential, or men with partners of child bearing potential, willingness to use adequate contraception during the treatment period and for a minimum duration of 5 months after last dose of nivolumab.
- 15) Maximal tumor resection has been performed as feasible.

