4.6 Response Evaluable Patients

All patients registered on the protocol and completing a minimum of one dose of nivolumab therapy followed by clinical or radiologic assessment of disease status.

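### The plan lets the baseline scan precede the required tumour resection, so surgical shrinkage can be scored as RECIST response in the ORR

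*Combined protocol and SAP*

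**What the plan says.** **Resection.** Inclusion criterion 15 (section 3.1) reads "Maximal tumor resection has been performed as feasible". It gives no date and no order relative to imaging.

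**Baseline imaging.** Section 4.5 wants baseline evaluations "performed as closely as possible to the beginning of treatment and never more than 42 days before the beginning of the treatment". Footnote 3 of the Study Calendar (section 2.3) says that "all tumor evaluation/measurement scans must be within 42 days prior to treatment". Both anchor the scan to treatment start only. Cystoscopy and biopsy have their own, wider window: "Screening cystoscopy and biopsy can be performed within 6 months of day 1" (footnote 7).

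**Response.** Section 4.5 applies RECIST to bladder lesions as well as nodes: "For measurable disease in the bladder and/or lymph node/s, RECIST criteria 1.1 will be used". All measurable lesions become targets, up to two per organ and five in total. PR is "At least a 30% decrease in the sum of diameters of target lesions, taking as reference the baseline sum of diameters"; CR begins with "Disappearance of all target lesions".

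**Who is counted.** Section 4.6 defines response-evaluable patients as those registered and "completing a minimum of one dose of nivolumab therapy followed by clinical or radiologic assessment of disease status". It does not require a post-resection baseline. Section 8.4.3 estimates ORR in that set and in all patients, with Wilson 95% intervals. Section 8.4.6 models CR/PR versus not on PD-1, PD-L1 and other markers.

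**The concern.** RECIST compares follow-up with a baseline that is meant to describe the disease at the start of study treatment. If a debulking operation falls between the baseline scan and day 1, the baseline sum describes tumour that is no longer there. The week-13 comparison then mixes the effect of surgery with that of nivolumab plus RT.

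The sequence is plausible. Section 4.1 accepts routine-care evaluations made before consent as screening evaluations if they fall within the window and local IRB policy permits. Section 1.4 describes pre-therapy staging scans as routine care. A staging CT taken before the resection can therefore qualify as the study baseline.

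At stake are the ORR, a single-arm estimate whose reader has no control group against which to notice the shift, and the odds ratios from 8.4.6, which are meant to inform a later study. Both would treat surgical reduction as treatment response.

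**Working it through.** **1. The plan's own figures.** The documents give no target, sample size or power for ORR. The only stated design figures concern 12-month PFS in section 8.3: 50% versus 75%, exponential times, 24 months' accrual, 12 months' follow-up, one-sided alpha 0.025, power 0.95.

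- Hazard ratio: ln(0.75)/ln(0.50) = 0.415.
- Event probability with uniform accrual: P = 1 − (e^(−12λ) − e^(−36λ))/(24λ), which gives 0.729 under the null and 0.430 under the alternative.
- n = [(1.960/√0.729 + 1.645/√0.430)/ln(0.415)]² = 29.8, so 30.
- Critical 12-month PFS at n = 30: 0.634 on the log-hazard scale, 0.643 on the cube-root scale; the plan states 0.64.
- Enrolment: 30/0.9 = 33.3, so 34.

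All are reproduced, and none takes ORR as an input.

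**2. Is the sequence allowed?** A CT on day −40 meets the 42-day limit. A resection on day −20 meets criterion 15. Treatment starts on day 1. No section requires the scan to follow the resection, asks for a repeat scan, or bars a lesion resected since the scan from the target list.

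**3. The response rule applied to one such patient** (illustrative sizes).

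- A bladder lesion of 40 mm on day −40 is resected to 20 mm on day −20 and does not change on study. Change at week 13: (40 − 20)/40 = 50% decrease, scored PR.
- The same lesion fully resected, with no other disease: scored CR.
- A small remnant that regrows to 25 mm by week 13: (40 − 25)/40 = 37.5% decrease, still PR. It is not PD by target-lesion measurement, because the calendar schedules no CT/MRI between pre-study and week 13 and the smallest recorded sum is the 25 mm itself.
- Nodes can dilute the effect. Add two nodal targets at the 15 mm minimum to the first case: the sum goes from 70 to 50 mm, (70 − 50)/70 = 28.6%, which is not PR. So not every affected patient is misclassified.

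**4. Effect on ORR.** Let p be the true ORR and f the share of patients in whom resection after the scan is enough on its own to meet PR or CR. The documents give neither. Assume p = 0.30 (9/30, Wilson 95% CI 17–48%) and f = 0.10 to 0.20 (3 to 6 of 30).

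| Case | Formula | f = 0 | f = 0.10 | f = 0.20 |
|---|---|---|---|---|
| Affected patients otherwise respond at the average rate | p + f(1 − p) | 30% | 37% | 44% |
| All affected patients would otherwise be non-responders (upper case) | p + f | 30% | 40% (12/30, CI 25–58%) | 50% (15/30, CI 33–67%) |

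With a higher true ORR the shift is smaller: at p = 0.50 the first formula gives 55% and 60%.

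**5. Effect on PFS.** Footnote 7 requires cystoscopy and biopsy at week 13, and section 4.9 counts residual invasive disease on post-therapy biopsy as progression. The tumour regrown to 25 mm in step 3 would normally be a PFS event by that route, whatever its RECIST category.

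**The case against.** The strongest reply is that existing wording already discourages the problem. Section 4.5 wants baseline evaluations near the start of treatment and target lesions that lend themselves to repeatable measurement, and a mass known to have been resected fits that poorly. The scan window is also short, so the resection must fall after the scan and inside the last 42 days. This makes the sequence less likely but does not forbid it: a scan on day −40 complies, and a site that follows the target-lesion rule literally would list the mass.

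A second reply is that little depends on it. ORR is secondary and estimated without a test, and the marker models are expressly exploratory. That stands, and it bounds the importance of the point. It does not remove it, because sites following the rules exactly would still record the wrong response.

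Two stronger readings are tempting. A reader might infer that resected tumour is in fact being counted and that the reported ORR is inflated. The documents show only that the order is permitted, not that it occurs or how often. A reader might also infer that hidden progression undermines the primary endpoint. The week-13 biopsy and the residual-disease rule largely close that route for invasive bladder disease. Moreover, a remnant under 10 mm is non-measurable, so even a correctly timed scan would give no target sum for the 20% growth rule.

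**Conclusion.** The gap is real and limited to response. Sections 2.3, 3.1 and 4.5 together permit scan, then resection, then day 1, and the response rule can then score the surgery as PR or CR. The bias can only raise ORR, and it carries into the 8.4.6 models. It arises from bladder target lesions only, since nodal targets are not removed by resecting the bladder tumour. N = 30, enrolment of 34 and the 0.64 critical value stand.

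The size cannot be derived from the documents. The 37–44% and 40–50% figures rest on an assumed 30% true ORR and on an assumed 10–20% of patients in whom surgery alone meets the threshold. The 40–50% range also assumes that none of them would have responded, so it is an upper case and not an expectation. If no scan precedes resection, the ORR is unchanged. The change is worth making because it is cheap and because, without a recorded resection date, the analysis could not show how many patients were affected.

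**What to change.** - **Section 4.5.** Add that a bladder lesion enters the baseline target sum only if it is measured on imaging done after the last pre-treatment resection. A bladder lesion resected after the only baseline scan is neither target nor non-target, and its absence or reduction at follow-up does not count toward CR or PR. Nodal lesions and any other unresected lesions are assessed as usual. Recording the resected lesion as non-target would not be enough: it would go from present to absent because of surgery and could again be read as response.
- **Sections 8.4.3 and 8.4.6.** Patients left with no assessable baseline lesion are excluded from the response-evaluable ORR and from the response models, are counted as non-responders in the all-patients ORR, and their number is reported. Section 4.6 needs a matching cross-reference.
- **Pre-study form.** Record the date of the last resection.

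Cost: a short addition to 4.5, a matching rule in the analysis sections and one data field, with no extra scan. A few patients leave the response-evaluable denominator, and the all-patients ORR becomes slightly conservative. The sample size and the primary analysis do not change.
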